Blast-exposed Veterans with Auditory Complaints, NCT02122458

Funding Agency: VA ORD, RR&D

Principal Investigator/Study Chair: [name].

Version 06/11/2017

Abstract

Clinical audiologists at the VA Pittsburgh Healthcare System (VAPHS) have observed a substantive increase in the number of veterans presenting with self-reported hearing problems but who demonstrate normal or near normal hearing sensitivity when tested with a standard audiotometric test battery. The primary complaint of these veterans is difficulty hearing speech in background noise, and preliminary clinical data have suggested poor performance on some tests of central auditory processing. Moreover, when fitted with mild-gain open-fit hearing aids, which amplify the high-frequency part of the speech spectrum, these patients have reported a reduction in their hearing-related problems. Nearly all of these veterans have reported histories of blast exposure and concussion while Operation Iraqi Freedom/Operation Enduring Freedom (OIF/OEF) deployed and described symptoms consistent with post-concussive syndrome. Similar auditory patterns for veterans with mTBI have been reported by clinical audiologists from other VA medical centers and military facilities although the auditory problems of this group of veterans have not been well described or studied (Fausti et al., 2009; Lew et al., 2007).

This study was developed in response to the clinical complaints offered by these veterans, with the goal being to better understand their problems by extensively assessing their auditory and auditory-related characteristics. A group of veterans with histories of blast exposure, histories consistent with mTBI, and normal audiotometric results, but notable auditory complaints will be evaluated with a standard audiotometric test battery, health status and quality of life questionnaires, auditory physiological test procedures, and behavioral central auditory processing tests. We also will administer speech perception and psychoacoustic tasks, and verbal working memory and language processing tests to better understand various aspects of their ability to hear, remember, and process speech and language through audition. A reading test that parallels an auditory language-processing task also will be administered to determine if any identified language processing problems are limited to the auditory system. Comparisons will be made to a control group of veterans who are negative for auditory and brain impairments, as well as to a group of veterans with Post Traumatic Stress Disorder (PTSD) but without histories of blast exposure or brain injury. In addition, the influences of coexisting PTSD will be examined. Secondarily, the benefit of fitting this population of veterans with mild-gain hearing aids that amplify the high-frequency part of the speech spectrum will be tested.

The information obtained from this study will be a first step in elucidating the problems of these veterans and will lay the groundwork for future studies that will focus on specific deficit mechanisms. This study also should contribute to the development of an effective assessment battery and interventions for this population.

List of Abbreviations

- ABR – Auditory Brainstem Response
ANOVA – Analysis of Variance
ANCOVA – Analysis of Covariance
APHAB – *Abbreviated Profile of Hearing Aid Benefit*
BSI-18 – Brief Symptom Inventory – 18 Item
BTBIS – *The Brief Traumatic Brain Injury Screen*
CCT – *California Consonant Test*
CRTT – *Computerized Revised Token Test*
CRTT-R – *Computerized Revised Token Test – Reading*
CRTT-R-Stroop – *Computerized Revised Token Test – Stroop*
CT – Computed Tomography
CPRS – Computerized Patient Record System
DDT – *Dichotic Digits Test*
DoD – Department of Defense
dB – Decibel
DPOAE – Distortion Product Otoacoustic Emissions

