Auditory problems experienced by blast-exposed warriors and veterans could relate to subclinical cochlear damage or indirect responses to damaged central auditory structures or compromised neural structures that subtend the auditory system. Poor processing of auditory signals also might reflect difficulties in cognitive functions secondary to or supported by the auditory system. For example, the reported difficulties might be due to reduced attention modulation of the auditory system or poor auditory working memory secondary to the brain injury. However, for some individuals their problems likely reflect global cognitive deficits that are most noticeable within the auditory domain. Common cognitive sequelae of TBI that might be related to or exacerbated by auditory dysfunction include difficulty comprehending complex language at pragmatic (Angeleri et al., 2008; Henchliffe et al., 1998) discourse (Coelho et al., 2002) and sentence levels (Henchliffe et al., 1998; Le Blanc et al., 2006). Sentence level processing has been identified as particularly vulnerable and sensitive to TBI. For example, Hinchliffe et al. (1998) found the Revised Token Test (McNeil & Prescott, 1978), a sentence level auditory processing test, to be the first factor selected in the identification of TBI, among 18 language factors investigated, and it predicted highly the other language and memory factors.

As suggested above, individuals with mTBI are at high risk for poor post-discharge outcomes. They often show decreased social and family integration and difficulty returning to work and school (Cattelani et al., 2002; Drake et al., 2000). Difficulty dealing with auditory information and background noise likely contributes to their poor outcomes, although no published studies have examined this relationship to date. Veterans targeted by the current study are unlikely to receive appropriate referral because even soldiers who have both peripheral hearing loss and mTBI have low referral rates to audiology clinical services (Helfer et al., 2011). Moreover, even if

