- d. Staggered Spondaic Word Test (SSW) to measure timing and inter-hemispheric processing of words
- e. Gaps in Noise Test (GIN) to assess temporal processing in noise
- f. Auditory brainstem response (ABR), middle latency response (MLR), long-latency response (LLR) and active event-related P300 to assess the electrophysiological status of the central auditory system.

Speech and Language Processing in Noise –

- a. The Words-in-Noise test (WIN; VA Compact Disk 4.0; Wilson & Burk, 2005) to target listening at the single word level
- b. The Listening in Spatialized Noise - Sentences Test (LiSN-S; Cameron & Dillion, 2012) to assess sentence perception in noise within a simulated 3-dimensional acoustic space
- c. Auditory and reading versions of subtests 1 through 10 from the Computerized Revised Token Test (CRTT and CRTT-R respectively; McNeil et al., 2009) will be administered in quiet and in +3 dB signal-to-babble to assess sentence level processing in both auditory and reading domains. The preliminary CRTT pretests will be administered prior to these tests to assure that the participants have the basic skills to complete the tasks and to measure baseline reaction time.

Executive Function –

- a. Digit span forwards and backwards both acoustically and visually according to Kemtes and Allen (2008) to assess verbal short term and computational memory skills
- b. The CRTT Stroop task (CRTT-R-Stroop; McNeil et al., 2010) to assess the interaction between language and executive function
- c. Rey Auditory Verbal Learning Test (Schmidt, 1996) to assess immediate and delayed verbal memory, efficiency of learning and the effects of interference
- d. Trail Making Test (Reitan, 1992) to measure attention and processing speed

PART 2 Procedures

Hearing Aid Fittings (treatment groups) – In Part 2 a subset of the participants from the mTBI-only and mTBI+PTSD groups from Part 1 will be fitted binaurally with open-fit hearing aids with mild high-frequency gain. Each group will consist of 25 participants. They will be randomly selected and randomly replaced if they decline to participate at any point during the treatment protocol.

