5.6 Data Analysis

Part 1 Analysis

Preliminary Analyses - The analysis will begin with basic descriptive statistics including means and standard deviations for continuous data and examination of distributional assumptions for all study measurements including the questionnaire data (e.g., HHIA, WHODAS-II, SSQ and HHIA-SO) for each group of interest. These analyses will be used to evaluate the extent of missing data and to identify outliers.

Primary Analyses - Random Forests (RF, Breiman, 2001) will be applied to determine which auditory, language processing, and executive function variables best discriminate the three groups. This technique performs variable selection and the variables are ranked by Gini score, a measurement of average accuracy of all trees containing a particular variable. One-way ANOVA will be used to determine differences between groups for normally distributed continuous data. Analysis of covariance (ANCOVA) will be used to adjust for differences between groups. If assumptions for the parametric test are not met, a non-parametric alternative will be used (e.g., Kruskal-Wallis, non-parametric ANCOVA). The p-values will be adjusted for multiple testing by using a false discovery rate method whenever more than one variable is being tested. Statistical assumptions (e.g., linearity, normality) will be verified prior to hypothesis testing. All statistical analyses will be two sided and the significance level will be 0.05.

Sample Size and Power - A sample size of 117 per veteran group will achieve 80% power at a 0.05 significant level to detect an effect size (i.e., odds ratio) of 2.50. This sample size was computed based on an adjustment that was made assuming that a multiple regression of the independent variable of interest on the other independent

variables in the model will result in an R-squared of 0.20. For one-way ANOVA, the total sample of 468 subjects achieves 80% power to detect an effect size of 0.18 or larger with a two-sided significance of 0.01 to account for multiple hypotheses testing. For analysis of covariance, the study is powered (0.80) to detect an effect size of 0.16 assuming the strength of the relationship between the response of interest and the covariates, measured as R-squared, is 0.20.

Part 2 Analysis

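### The reading test is meant to show whether language problems are confined to hearing, but the Part 1 analysis has no test that compares the auditory and reading scores

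*Combined protocol and SAP*

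**What the plan says.** The Abstract says the reading test is given "to determine if any identified language processing problems are limited to the auditory system". Section 2.0 names the rival explanation: "for some individuals their problems likely reflect global cognitive deficits that are most noticeable within the auditory domain".

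Section 5.1 (Speech and Language Processing in Noise) gives the same participants "Auditory and reading versions of subtests 1 through 10 from the Computerized Revised Token Test", the CRTT and CRTT-R, in quiet and in babble at +3 dB, "to assess sentence level processing in both auditory and reading domains". Digit span is also given acoustically and visually. Its stated purpose is short-term and computational memory.

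Section 5.6 (Part 1, Primary Analyses) lists these methods:
- random forests, to rank variables by Gini score;
- group tests: "One-way ANOVA will be used to determine differences between groups for normally distributed continuous data";
- covariate adjustment: "Analysis of covariance (ANCOVA) will be used to adjust for differences between groups", with no covariates named;
- non-parametric versions where assumptions fail;
- p-values "adjusted for multiple testing by using a false discovery rate method whenever more than one variable is being tested".

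The level is set by "All statistical analyses will be two sided and the significance level will be 0.05". The only interaction in section 5.6 is group by time, in the Part 2 mixed model.

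**The concern.** Whether a problem is confined to one modality is a question about two scores in the same person. Section 5.6 has no modality factor, no group-by-modality term, no auditory-minus-reading contrast, no bound for an acceptable reading deficit and no decision rule. What remains is a group test on each score.

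One significant and one non-significant result do not show that the two deficits differ. A non-significant reading result does not show that reading is intact. A global deficit could therefore be reported as auditory-specific by chance, and a real but smaller reading deficit could be reported as absent. The study is meant to inform an assessment battery and later interventions, and auditory-specific and global deficits point in different directions for both.

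**Working it through.** **Inputs from the plan.** Four groups of 117 (468 in total), one-way ANOVA, analysis level 0.05 with false discovery rate control, and power computed at 0.01 for f = 0.18.

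**Assumptions, not in the documents.** The correlation between CRTT and CRTT-R (0.5 to 0.7 below), the sizes of the deficits, normal scores on a common standardised scale, and both mTBI groups shifted equally against the other two. With two groups shifted by d SD, the group means lie d/2 either side of the grand mean, so f = d/2. The design effect of 0.18 is thus d = 0.36 SD, and d = 0.30 SD is f = 0.15.

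**Step 1. The plan's own figure.** Non-central F with df = (3, 464) and non-centrality f² × N = 0.18² × 468 = 15.2. At alpha 0.01 the power is 0.783, and f = 0.183 gives 0.80. The stated 80% is reproduced to rounding.

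**Step 2. A check without simulation.** With equal deficits at f = 0.18 and uncorrelated scores, the chance that the auditory test is significant and the reading test is not is 0.783 × (1 − 0.783) = 0.170 at alpha 0.01. At 0.05 it is 0.918 × 0.082 = 0.075.

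**Step 3. Correlated scores.** I simulated 30,000 trials per setting. *Auditory only* means auditory ANOVA significant, reading ANOVA not. *Difference* means the one-way ANOVA on the within-person auditory-minus-reading score is significant.

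| True deficits, auditory / reading (SD) | r | Auditory only, 0.01 | Auditory only, 0.05 | Difference, 0.01 | Difference, 0.05 |
|---|---|---|---|---|---|
| 0.30 / 0.30 | 0.5 | 16.9% | 12.6% | 0.9% | 4.9% |
| 0.30 / 0.30 | 0.7 | 13.1% | 9.6% | 1.0% | 5.1% |
| 0.36 / 0.36 | 0.5 | 12.2% | 6.0% | 1.0% | 5.1% |
| 0.36 / 0.36 | 0.7 | 9.5% | 4.6% | 1.0% | 5.0% |
| 0.36 / 0.18 | 0.5 | 64.6% | 58.9% | 15.0% | 34.1% |
| 0.36 / 0.18 | 0.7 | 63.4% | 57.7% | 30.0% | 53.8% |

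In the first four rows there is no modality difference, so an auditory-only conclusion is false. In the last two the auditory deficit is larger, but reading is impaired, so *limited to* audition is still false.

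**Step 4. Power of the proposed test.** For a true auditory-only deficit (0.36 / 0 SD, 10,000 trials), the difference test has power 0.78 at r = 0.5 and 0.97 at r = 0.7 at alpha 0.01, and 0.92 and 0.99 at 0.05. It is weak if the scores are uncorrelated (0.38 at alpha 0.01).

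**Step 5. Unequal reliability.** Suppose one common latent deficit of 0.8 SD and reliabilities of 0.9 (auditory) and 0.6 (reading), all assumed.
- Observed deficits: 0.8 × √0.9 = 0.759 and 0.8 × √0.6 = 0.620.
- Correlation: √(0.9 × 0.6) = 0.735. SD of the difference: √(2 − 2 × 0.735) = 0.728.
- Standardised difference: 0.139 / 0.728 = 0.191, so f = 0.096 and non-centrality is about 4.3.
- The difference test then rejects in about 18% of trials at 0.01 and 38% at 0.05, although the latent deficit is the same in both modalities.

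**Step 6. Precision for reading.** For one mTBI group against controls, the 95% half-width is about 1.96 × √(2/117) = 0.26 SD.

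**The case against.** Much of the case on the other side stands.

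- **No stated rule.** A reader might infer that the plan commits to a separate ANOVA for each modality and to a two-p-value conclusion. It does not. Section 5.6 never mentions the CRTT, the CRTT-R or modality. The error rates above are conditional on reading the results that way. The firm point is that no other inferential route is given: Gini ranking tests no modality difference, and ANCOVA has no named covariates and a different stated purpose.
- **Both tests significant.** A reader might infer that the plan also fails when both modalities are impaired and the auditory deficit is larger, say 0.8 against 0.4 SD. The Abstract asks only whether problems are limited to audition. Here they are not, and two significant ANOVAs (about 88% of trials at alpha 0.01) give the right answer. In this case a significant difference score alone would mislead: at r = 0.7 it is significant in 99% of trials.
- **Choice of inputs.** The error depends on deficit size and threshold. At 0.36 SD and an unadjusted 0.05, the false pattern (5 to 6%) is no more frequent than the difference test's own error. The effective threshold under false discovery rate control depends on the other tests.
- **Digit span and babble.** A reader might infer that the two digit spans exist to separate auditory from global deficits, or that babble scores mean nothing for reading. Section 5.1 gives the spans a memory purpose and gives both Token Test versions in babble by design. Babble may act as a distractor during reading.
- **Importance.** The auditory-reading contrast is not spelled out in Specific Questions a to e, and the study calls itself a first step. That limits the weight of the point but leaves a stated purpose without a matching analysis.

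**Conclusion.** The concern holds as a gap between a stated purpose and the analysis. The reading test is there to show whether language problems are confined to hearing, and Part 1 contains no test that compares modalities and no rule for the conclusion.

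If separate p-values fill the gap, a false auditory-only result is roughly 13 to 17 times as frequent as with a difference test at alpha 0.01 for equal 0.30 SD deficits, and about twice as frequent at 0.05. At the design effect the excess remains at 0.01 and vanishes at 0.05. The larger risk is the partial reading deficit, which would be missed in well over half of trials at either level. These sizes rest on assumed deficits, assumed correlations and unadjusted thresholds. The stated ANOVA sample size is not in error, and the study's other aims are unaffected.

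**What to change.** Add to section 5.6, Part 1:

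1. A group-by-modality test for CRTT against CRTT-R, using each participant's difference between scores standardised to the control group's mean and SD. Make quiet the primary contrast. Keep babble as a secondary contrast or as a third factor (group by modality by noise).
2. A decision rule. Claim a deficit limited to the auditory system only if the difference is significant **and** the confidence interval for the reading deficit lies within a pre-specified bound. If only the difference is significant, claim a deficit larger in audition.
3. A justification of the bound. With a half-width of about 0.26 SD for one mTBI group against controls, a tighter bound could not be met even if the observed reading deficit were zero.
4. Optionally, acoustic minus visual digit span as supporting evidence.
5. A stated limitation: the difference score assumes that the two tests are similarly sensitive and reliable.

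The cost is a few sentences and a few more tests in the false discovery rate family. No new visits, participants or measurements are needed.

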2.0 Introduction

BACKGROUND AND SIGNIFICANCE

Between October 1, 2001 and December 31, 2012 a total of 1,599,575 unique OEF/OIF and Operation New Dawn (OND) military personnel separated from active duty and became eligible for benefits through the Veterans Health Administration (Department of Defense, Defense Manpower Data Center, 2013). Utilization data suggested that approximately 56% of these veterans have accessed some level of VA healthcare services, which is in contrast to the 28-24% utilization rate by the overall veteran population (National Center for Veterans Analysis and Statistics, 2013). Among this population of veterans, traumatic brain injury (TBI) and post-traumatic stress disorder (PTSD) are evident at high rates and frequently are comorbid conditions. Moreover, these two conditions are associated with substantially elevated healthcare costs. Auditory problems are a common complaint among veterans with TBI and PTSD even when hearing is normal upon standard audiotometric testing; yet optimal methods for diagnosis and treatment of their auditory problems have not been well established or studied. Understanding and improving their auditory function could advance their interactions within the VA healthcare system, positively impact the services that they receive, affect their abilities to work and learn, and improve their quality of life.

Mild Traumatic Brain Injury

Traumatic brain injury is considered a signature injury of current and recent U.S. military engagements largely due to blast injuries (Wilk et al., 2010). An estimated 20% of soldiers with blast injuries suffer from acute TBI with most cases being mild (Armed Forces Health Surveillance Center, 2010). It is a significant healthcare issue among veterans with 10 to 15% of all OIF/OEF veterans having mTBI; a prevalence rate substantively higher than in the civilian population (Hoge et al., 2008). Sensory problems, such as hearing and vision loss are common in persons with mTBI especially

in persons with injuries due to blast exposure. In the acute phase, individuals with mTBI complain of difficulties with headache, tinnitus, dizziness, nausea, fatigue, hypersensitivity, irritability, memory deficits, and depression (Sheedy et al., 2006). Cognitive deficits can be of the magnitude to interfere with daily activities (Alexander, 1995) and typically include problems of attention and working memory (McAllister et al., 2006), processing speed, verbal fluency (Ruff et al., 2010), comprehension and production of complex connected language (LeBlanc et al., 2006) and areas of executive function (Belanger et al., 2005). Most adults with mTBI make a favorable recovery within days to weeks of injury but those with more severe injuries are inclined to exhibit persistent neuropsychological deficits (Bilger, 2008; Iverson et al., 2007). The expression of symptoms is variable and a substantial number of individuals diagnosed with mTBI do not exhibit frank impairments upon neuropsychological testing (Tombaugh et al., 2007), although others will be symptomatic on both behavioral and neurophysiologic tests (Ruff et al., 2010). An added complexity is that post-concussive symptoms associated with mTBI can manifest months or even years after the insult (Bales et al., 2009; Terrio et al., 2009). These persistent and later emerging symptoms can result in long-term impairments of daily function with as many as 43% of individuals hospitalized for TBI reporting at least one unmet rehabilitative need at 1-year post-injury (Corrigan et al., 2010). The delayed onset of symptoms might represent a gradually-emerging consequence of the brain injury or a failure to detect persistent subclinical neurobehavioral signs of the injury (Ivins et al., 2009). Regardless of whether these potentially handicapping symptoms are unidentified or late emerging, they represent a significant concern among returning OIF/OEF warriors and veterans. Similar findings are expected for veterans who only served in OND but their overall numbers are expected to be considerably smaller.

Blast Injury

Blasts have been responsible for about two-thirds of all combat injuries in the OIF/OEF conflicts (Murray et al., 2005), and although blast injuries have long been associated with modern warfare, the expansion of insurgent and terrorist tactics in these recent conflicts has been linked to increasing numbers of injuries and deaths due to the use of improvised explosive devices. The blasts from these and other types of explosive devices are complex, as are the resulting injuries (Kocsis & Tessler, 2009; Wightman & Gladish, 2001). Upon detonation there is rapid conversion of the explosive (solid or liquid) into gases that expand rapidly and in turn compress the surrounding air. This initial pressure pulse is referred to as the blast overpressure. As the gases continue to expand the air pressure drops behind the pressure pulse creating a relative vacuum or blast underpressure, which reverses the direction of the blast forces. With high explosives the blast occurs instantaneous and the pressure waves propagate faster than the speed of sound. Acoustic energy is compressed in front of the pressure pulse and eventually the blast waves deteriorate into acoustic waves (Wightman & Gladish, 2001). These extreme pressure changes can produce a shattering effect and barotrauma, which are considered the primary blast injuries. Barotrauma results from excessive stretching and shearing due to differential acceleration and deceleration across the body relative to density. The gas and fluid-filled structures of the body, such

as the lungs, bowel, and the middle ear are believed to be most vulnerable (Kocsis & Tessler, 2009).

In warfare the injuries from blasts are heterogeneous and confounded by the secondary (projectiles), tertiary (effects of wind), and quaternary (burns, asphyxia, toxins) effects of blasts (DePalma et al., 2005; Wightman & Gladish, 2001). Objects propelled by the energy of the explosions strike victims and cause blunt or penetrating ballistic trauma. Bodies can be propelled by the force of the blast and strike objects, and victims can be injured by structures collapsing onto them. Additional injury can occur due to inhalation of toxic gases and exposure to chemicals resulting from the explosives, as well as resulting heat, fire and smoke. Severe head injury is the leading cause of death due to blast with subarachnoid and subdural hemorrhage being the most common finding. The brain is somewhat protected from the blast pressure waves because its water density is homogeneous but stress waves are capable of penetrating the skull (Chavko et al., 2007) and in extreme cases can shatter the cranium from within (Wightman & Gladish, 2001). Brain injury also can occur as a consequence of injuries to other vulnerable organs, such as the lung, gastrointestinal track, heart, and long bones, producing air emboli, fat emboli, increased venous pressure, and hypoxia/ischemia that can result in more brain damage than the blast itself (Mayorga, 1997). Because the brain is protected from the forces of the blast wave, most blast-related head injuries are believed to be secondary, tertiary and quaternary injuries (DePalma et al., 2005; Wightman & Gladish, 2001). Yet evidence is mounting that the brain and spinal cord incur primary blast injuries from the pressure wave itself, although the injury mechanisms are unclear. Furthermore, because of the advanced body armor worn by soldiers, damage to the central nervous system from combat-related blasts is increasingly attributed to the primary effects of the blast (DePalma et al., 2005; Haberstroh, 2004).

Experimental animal models using shock and blast tubes have shown alterations of the central nervous system that are consistent with primary blast injuries. Connell et al. (2011) used a guinea pig model and demonstrated that blast waves compress neural tissue and produce axonal membrane damage. Similar studies with rats and rabbits have produced myelin disruption, diffuse axonal damage, neuronal degeneration and increased oxidative stress (Cernak et al., 2001). Blast injuries in animals also have been associated with behavioral changes and long-term learning deficits.

Of the veterans exposed to blasts and associated acoustic trauma, neuropathologic changes have been reported and include small hemorrhages within white matter, chromatolytic changes in neurons, diffuse brain injury and subdural hemorrhage at the frontal and parietal convexities (Taber et al., 2006). Diffuse axonal injuries also occur often in the frontotemporal areas, the internal capsule, deep grey matter (such as the basal ganglia), upper brainstem and the corpus callosum. Computer simulations have suggested that high stresses caused by primary pressure waves are associated with coup and contrecoup damage (Chafi et al., 2010) with orbitofrontal regions and the posterior fossa (cerebellum and brainstem) particularly susceptible. Injuries also can be due to system reaction to the initial brain insult, such as swelling and oxidative stress.

In cases of mTBI many of the lesions and changes in brain matter remain undetected on MRI or CT scans (Niogi & Mukherjee, 2010), although improved imaging techniques are proving sensitive to the unique neurological abnormalities of this population. MacDonald et al. (2011) used diffusion tensor imaging and showed marked abnormalities in the middle cerebellar peduncles, cingulum bundles, and the orbitofrontal white matter when testing military personnel with blast-related mTBI, although their participants were mixed relative to the type of injury. Davenport et al. (2012) studied two groups of OIF/OEF veterans with mTBI. One group had mTBI due to blast exposure whereas the other group had non-blast related brain injuries. They also used diffusion tensor imaging and found white matter disruptions with both groups but the disruptions were more diffuse with the blast-exposed veterans. Moreover, the disruptions were more pervasive with increased number of blast exposures. Multiple blast exposures is an issue with the OIF/OEF veteran population because military personnel with mild concussions often return to full duty status shortly after injury with about 85% being re-injured within 3 months of returning to duty (MacGregor et al., 2011).

Auditory Impairment and mTBI

Hearing and visual impairments are common in persons with TBI and likely contribute to their communication, social and employment handicaps. Furthermore, the more severe the TBI the more marked hearing loss tends to be, especially for high-frequency test signals. Peripheral hearing loss is commonly associated with TBI particularly in blast injury cases with concurrent abnormalities of the central auditory system noted in some individuals (Fausti et al., 2009; Lew et al., 2007). As indicated above, blast pressure waves can affect both fluid and gas filled structures, such as the ear, with the proximity and intensity of the blast influencing the magnitude of the injury (Lew et al., 2007; Patterson & Hamernik, 1997). In the OIF/OEF conflicts, tinnitus and hearing loss have been responsible for the largest number of primary disabilities, with auditory problems being the fourth leading cause of medical referral for combatants returning from deployment (McIlwain et al., 2008). Moreover, veterans with blast-related mTBI are more likely to have auditory complaints than non-blast related mTBI (Belanger et al., 2011). Auditory system injuries also are the most common single type of injury consequent to blast exposure, resulting in tympanic membrane perforation and middle ear and cochlear damage (Gondusky & Reiter, 2005; Patterson & Hamernik, 1997). In a review of veterans' post-deployment hearing status, Helfer et al. (2005) found that post-combat veterans were 50 times more likely to have ear-related problems than those who did not have combat experiences. However, most of the reported auditory problems were peripheral in nature, usually middle ear and cochlear, and not necessarily associated with documented TBI (Gondusky & Reiter, 2005).

Complaints of auditory problems with no peripheral hearing loss have been reported in individuals with known mTBI but their auditory complaints have not been studied widely or systematically, nor have effective treatments been established (Fausti et al., 2009; Lew et al., 2007). Nonetheless, a recent publication by [name] et al. (2012) reported on

standard audiometric and central auditory assessment results from 36 hospitalized OIF/OEF warriors with histories of blast exposure and a similar group of non-hospitalized veterans with no blast exposures. All of the blast-exposed warriors had been evaluated for TBI with 19 of 36 having a diagnosis of TBI, and upon interview, 13 also indicated that they had symptoms of PTSD. Although hearing handicap was not measured, 39% reported increased difficulty hearing in quiet and 78% reported more difficulty hearing in noisy environments since their blast exposures. As expected, the two groups were similar and within normal limits on the standard audiometric measures, but differences emerged on some, but not all of the central auditory measures. The blast-exposed patients were most notably different on several behavioral measures of central auditory processing and speech perception in noise (i.e., Gaps-in-Noise, Masking Level Difference, Staggered Spondaic Words, QuickSIN) and a long latency event-related potential test. It should be noted, however, that on none of these tasks did a majority of the blast-exposed warriors demonstrate abnormal results. Furthermore, no soldier produced abnormal results on all of the central auditory tests, suggesting substantial group heterogeneity. The composition of the blast-exposed group likely contributed (e.g., not all reported auditory complaints), but possible differences in the extent and location of the blast-related damage were considerations and highlight the complexity of this group of patients.

Auditory problems experienced by blast-exposed warriors and veterans could relate to subclinical cochlear damage or indirect responses to damaged central auditory structures or compromised neural structures that subtend the auditory system. Poor processing of auditory signals also might reflect difficulties in cognitive functions secondary to or supported by the auditory system. For example, the reported difficulties might be due to reduced attention modulation of the auditory system or poor auditory working memory secondary to the brain injury. However, for some individuals their problems likely reflect global cognitive deficits that are most noticeable within the auditory domain. Common cognitive sequelae of TBI that might be related to or exacerbated by auditory dysfunction include difficulty comprehending complex language at pragmatic (Angeleri et al., 2008; Henchliffe et al., 1998) discourse (Coelho et al., 2002) and sentence levels (Henchliffe et al., 1998; Le Blanc et al., 2006). Sentence level processing has been identified as particularly vulnerable and sensitive to TBI. For example, Hinchliffe et al. (1998) found the Revised Token Test (McNeil & Prescott, 1978), a sentence level auditory processing test, to be the first factor selected in the identification of TBI, among 18 language factors investigated, and it predicted highly the other language and memory factors.

As suggested above, individuals with mTBI are at high risk for poor post-discharge outcomes. They often show decreased social and family integration and difficulty returning to work and school (Cattelani et al., 2002; Drake et al., 2000). Difficulty dealing with auditory information and background noise likely contributes to their poor outcomes, although no published studies have examined this relationship to date. Veterans targeted by the current study are unlikely to receive appropriate referral because even soldiers who have both peripheral hearing loss and mTBI have low referral rates to audiology clinical services (Helfer et al., 2011). Moreover, even if

referred, they have a reduced likelihood of receiving adequate auditory rehabilitative services due to their normal performance on standard audiotmetric test measures. Yet, given the elevated incidence of mTBI in military and veteran populations, the scope of this problem is certain to grow as the remaining OIF/OEF warriors convert to veteran status and age-related hearing loss confounds their auditory processing difficulties. A reflection of this increase is the formation of an online Auditory Processing Disorder group consisting of 36 VA audiologists who correspond regularly by email about how to best assess and treat these veterans. Consistent concerns expressed by this group have related to test battery composition and management of patients once they have been identified and diagnosed.

Post-Traumatic Stress Disorder and mTBI

The coexistence of PTSD with mTBI is a confounding factor in OIF/OEF veterans with blast-related mTBI. Hoge et al. (2008) found that approximately 44% of the returning OIF/OEF soldiers who reported loss of consciousness following blast injury met the criteria for PTSD. In a similar study, Pietrzak et al., (2009) observed that approximately 65% of their sample of OIF/OEF veterans with mTBI screened positive for PTSD, although loss of consciousness was not a strong predictor of comorbid PTSD, as was observed in the Hoge et al. (2008) study. A range of psychosocial, somatic and cognitive problems are characteristic of PTSD such as flashbacks, nightmares, hyperarousal, and avoidance of stimuli related to traumatizing events, but a number of symptom overlap with mTBI including impaired concentration, headaches, irritability, anger and sleep disturbances (Ruff et al., 2010). Persons with PTSD and mTBI also tend to experience problems with memory and appropriate modulation of attention. Veterans with both mTBI and PTSD also fair worse than veterans with isolated impairments in that they have greater health and psychosocial difficulties, poorer quality of life, and perceive themselves as having greater barriers to mental healthcare. They also are more likely to experience employment and marital problems and unmet psychosocial needs. Pietrzak et al. (2009) found that PTSD and related psychiatric conditions such as depression mediate the physical and post-concussive symptoms observed in mTBI veterans, suggesting that appropriate treatment of depression and PTSD symptoms might improve functional recovery of veterans with mTBI. It also is possible that problems with hearing, which tend to increase the likelihood and severity of depression, can interfere with the treatment of mTBI and PTSD.

Background Noise

